#### 4.2. TMS stimulation and EEG recording

EEG data will be recorded using a 64-channel TMS-compatible electrode cap (Easy Cap). Signals will be collected at 2000Hz (impedance: <5k $\Omega$ , low-pass filter: 0.1-500Hz) during pre- and post-TMS stimulation epochs (-100ms to 200ms). Fifty suprathreshold TMS pulses will be applied to M1 while the subject is seated quietly with eyes open. This procedure will be conducted bilaterally at each assessment timepoint. Peripheral auditory and somatosensory stimulation effects will be minimized to avoid EEG artifact. Single-channel evoked potentials will be defined as the area under the curve obtained between 10 and 150ms poststimulus. These TMS-evoked potentials will be used to index local M1 excitability and connectivity with the contralateral homotopic region. As a secondary exploratory analysis, EEG recording will also be captured during motor performance using a joystick task.

#### 4.3. TMS data analysis:

Peak to peak MEP amplitudes will be measured off-line. Recordings with EMG background activity will be excluded from further analysis. Data analysis SICE, SRC, rIHI, aIHI, and mapping: Peak to peak MEP amplitudes will be measured off-line. Recordings with EMG background activity will be excluded from further analysis. For

the SRC, the mean MEP amplitudes at each stimulus intensity will be calculated. For SICE, rIHI and aIHI, mean MEP amplitudes elicited at different ISIs and CS intensities will be calculated as a percentage of the mean test MEP amplitude evoked by TS alone. CS intensities will be expressed as percentage of the subject's MT. For mapping, the area will be calculated as the number of stimulation sites that produce an MEP in of the trials. The center of gravity (CoG), an estimate of the center of the map, will be calculated for each target muscle (ECU or FCU) based on the weighted MEP amplitudes at each active location. Statistical analysis: We will use linear mixed models to quantify the effects of subject type (cortical stroke patient, subcortical stroke patient, healthy control) along with other, measure-specific factors (outlined below) on outcomes of interest. The analyses will incorporate models of within-subject correlations stemming from multiple measures on each subject. Hypothesis testing will be conducted on mean model parameters at a significance level  $\alpha = 0.05$ . Post-hoc analysis will be corrected for multiple comparisons. For SICE: A mixed model will assess the effect of subject type and stimulated hemisphere (ipsi- or contralesional for the stroke subjects, zero for the controls) along with repeated measure CS intensity (60%, 80% MT) on relative conditioned MEP amplitude. For rIHI: A mixed model will be used to determine the dependence of relative conditioned MEP amplitude on subject type along with the repeated measures inhibition (cl\_M1 on il\_M1 and il\_M1 on cl\_M1) and ISI (2ms, 10ms). For aIHI: We will perform a mixed model analysis to determine the dependence of relative conditioned MEP amplitude on subject type along with the repeated measures inhibition (as above), time after go signal (0ms, 300ms, 400ms, and 450ms), and target size (small, extra-large). For SRC: The effect of the repeated measure stimulus intensity on the average MEP

amplitude, along with subject type and stimulated hemisphere (as above), will be examined. We will evaluate linear and nonlinear trends of MEP amplitude across intensity levels and will consider various parsimonious parametric structures for the variance-covariance matrix. *For MT*: A mixed model will quantify the effect of subject type (as above) and repeated measure stimulated hemisphere (as above) on MT. *For Mapping*: A mixed model will quantify the effect of subject type (as above) and repeated measure stimulated hemisphere (as above) on the area and CoG of the maps for both ECU and FCU. Furthermore, exploratory analyses and advanced statistical techniques will be used to investigate the relationship between the area and CoG of the maps (i.e., muscle representations at rest) and task-based fMRI activation patterns (i.e., muscle representations during movement).

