#### 4.1.4. TMS stimulation and EMG recording

Subjects will be comfortably seated in a dental chair surrounded by a frame that carries a coil holder to assist with the application of TMS to the brain. The MRI of the brain will be reconstructed for neuro-navigation assisted TMS of the brain using Brainsight (Brainsight, Rogue Research, Montreal, Canada). Surface electromyographic (EMG) (bandpass 1 Hz – 1 kHz) activity will be recorded from the target muscle (right and left extensor carpi ulnaris (ECU) and flexor carpi ulnaris (FCU) muscles and other muscles as needed for control), using surface electrodes (11 mm diameter) in a belly-tendon montage and a data acquisition system (LabVIEW, National Instruments, CA, USA). A picture of the subject's arm will be taken to help ensure consistent electrode placement across days. TMS will be applied through an air-cooled figure of eight-shaped coil (7 cm wing diameter) using the rapid Magstim200^2 (Magstim Company, UK). The coil will be positioned on the scalp over the left M1 at the optimal site (hot spot) for stimulating the right ECU. At the optimal site, the resting motor threshold (MT), defined as the minimum stimulus intensity to evoke an MEP of >50  $\mu$ V in at least five

of ten trials (Rossini et al. 1994b), will be determined to the nearest 1% of maximum stimulator output (MSO). The position will be marked on a standard MRI of the brain in Brainsight to ensure coil stability during the experiment.

*Interhemispheric inhibition* : For the measurements of interhemispheric inhibition (IHI) two Magstim 200 stimulators (Magstim Company, UK) will be used. With the subjects at rest, a conditioning pulse (CS) will be applied to the optimal scalp position of the M1 of either hemisphere to stimulate the corresponding contralateral ECU muscle using a figure of eight coil (70 mm diameter) (Ferber et al. 1992). The intensity of CS will be adjusted to produce a MEP of about 1.5 mV (Ferber et al. 1992). A test pulse (TS) will be applied to the homotopic area of the opposite hemisphere, defined as optimal scalp position to stimulate the contralateral ECU using a smaller figure of eight coil (50 mm diameter). The intensity of the TS will be adjusted to produce a MEP of about 1.5 mV (Ferber et al. 1992). Paired pulses at different ISIs will be intermixed with single TS and single CS and applied at random.

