*Short interval cortical inhibition*: TMS will be applied through a figure of eight-shaped coil (7 cm wing diameter) using two Magstim 200 stimulators connected via a Bistim module (Magstim Company, UK). Short interval cortical inhibition (SICI) will be measured using paired pulse TMS at an ISI of 2 ms. The intensity of the CS will be varied between 30 and 80% of MT and will be administered randomly (Butefisch et al. 2003; Butefisch et al. 2008) while the intensity of TS will remain suprathreshold. Paired pulses will be intermixed with single test- and conditioning pulses and administered

randomly to M1 of either left or right hemisphere. The sequence of timing of stimuli will be controlled by customized software.

*Active Interhemispheric inhibition:* Active interhemispheric inhibition (aIHI): Active IHI will be measured during the pre- movement time period of a pointing task. In this task subjects have to manipulate a joystick in response to a visual target presented on a computer screen. Real-time feedback about the joystick position is provided by a cursor moving on a computer screen. Subjects will be instructed to move the cursor as quickly as possible to the center of a target square immediately upon its appearance on the screen with a preset time of 2s for movement completion. Feedback (“hit” or “miss”) will be given depending on their ability to move the cursor is in the center of the target within a pre set time of 2 sec. This task was previously reported in detail by our group but modified to allow its manipulation by patients with more impaired hand function and automatic indication of the movement time. This adjustment eliminates the need for selective finger function. For aIHI measures, CS and TS will be applied at the time of the target presentation, 300, 400 or 450 ms after the target presentation at the same ISIs and intensities described for the rIHI.

*Cortical Mapping:* TMS will be applied through a figure of eight-shaped coil (7 cm wing diameter) using the rapid Magstim200^2 (Magstim Company, UK). Motor maps will be derived for the right and left ECU and FCU muscles. A rectangular grid consisting of stimulation sites spaced at least 0.5 cm apart will be superimposed on the subject’s MRI and centered on the subject’s hotspot for a given muscle. EMG activity

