## **5. Participant Selection:**

*Stroke patients:* For SAs # 1-2, subjects will be adult females and males, ages 40-80 years with (1) one cerebral ischemic infarction < 1 month affecting the primary motor output system of the hand at a cortical (M1) level as defined by MRI of the brain, (2) paresis of the hand for more than 3 days after their cerebral infarction ( $MRC \leq 4$ - of wrist- and finger extension/flexion movements), (3) extension of the wrist ( $MRC \geq 3$ , > 10 degree) at the time of the enrollment into the study, (3) no other neurological disorders, (4) no aphasia that prevents subjects from following instructions or their inability to communicate effectively with the study team, (5) no or only mild cognitive impairment but not to the level of dementia (RBANS(Randolph et al. 1998)), (6) no or only mild depression (Hamilton Depression score of <19) (7) no contraindication to TMS or MRI, (8) no intake of CNS active drugs that blocks plasticity (9) the ability to give informed consent. We have chosen this age range because stroke is a disease of elderly people. Only 8.9% of ischemic strokes affect people under the age of 50 years(Fonarow et al. 2010). As plastic changes are likely age-dependent (Sawaki et al. 2003), we would like to exclude “age” as a possible confounding factor by matching our patients post-stroke to the healthy controls (data gathered under R56 NS070879-01) thereby avoiding the possibility that older age may result in a false negative result in our stroke patients.

**Healthy Subjects:** We will study 30 healthy adult females and males, ages 40- 80 years with no neurological or psychiatric diseases and a normal neurological examination, normal MRI of the brain and normal neuropsychological testing(Randolph et al. 1998), no intake of CNS active drugs, no contraindication to TMS and ability to give informed consent.

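### The active IHI model omits ISI although active IHI is acquired at the same ISIs as resting IHI, so as written it averages over ISIs and halves any group effect confined to one of them

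*Combined protocol and SAP*

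**What the plan says.** All references are to the combined protocol and SAP.

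- **Acquisition, resting IHI (section 4.1.4).** More than one ISI is used: "Paired pulses at different ISIs will be intermixed with single TS and single CS and applied at random". The values are not given there.
- **Acquisition, active IHI (section 4.1.4).** Pulses are delivered at four times relative to target presentation, "at the same ISIs and intensities described for the rIHI".
- **Data reduction (section 4.3).** "For SICE, rIHI and aIHI, mean MEP amplitudes elicited at different ISIs and CS intensities will be calculated as a percentage" of the response to the test pulse alone. ISI-level aIHI values therefore exist before any model is fitted.
- **Resting IHI model (section 4.3).** The repeated measures are inhibition direction "and ISI (2ms, 10ms").
- **Active IHI model (section 4.3, the next sentence).** The factors are subject type, inhibition direction, "time after go signal (0ms, 300ms, 400ms, and 450ms), and target size (small, extra-large"). ISI is not listed. The cross-reference back to the resting model is attached to inhibition direction only.

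The general statement in section 4.3 introduces these lists as "measure-specific factors (outlined below"), so they are the specification for each measure. Section 4.4, Study #2, says its tests follow those of Specific Aim 1 and adds acquisition time and time post-stroke. It supplies no ISI term for aIHI.

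**The concern.** The plan treats ISI as a factor worth modelling at rest, then leaves it out of the model for the same measurement during movement preparation, without giving a reason. If responses at both ISIs enter the model as written, they act as replicates of one cell. Two things follow. The systematic difference between ISIs goes into the residual. Every group, direction and timing effect becomes an average over ISIs.

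The averaging matters only if the effect differs between ISIs. A difference between stroke patients and controls that is present at one ISI and absent at the other would be shrunk and could be missed. The model would give no sign of this, because it has no term that could show it. The text also leaves open whether 2 ms, 10 ms or their average is the result to be reported, and that choice should be made before the data are seen.

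**Working it through.** The plan states no power, effect size or SD for aIHI, so there is no figure to reproduce. The check has four steps.

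**1. Cells acquired against cells modelled.** The inputs are 2 inhibition directions, 4 times and 2 target sizes (aIHI model, section 4.3), and 2 ISIs (resting model, section 4.3, linked to aIHI by the acquisition text in section 4.1.4). Assuming full crossing:

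- Acquired: 2 × 4 × 2 × 2 = 32 conditioned cells per subject.
- Described by the model: 2 × 4 × 2 = 16.

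**2. Size of the averaged effect.** Let the group difference be d at one ISI and 0 at the other. With equal weight on the two ISIs, the estimated difference is (d + 0)/2 = d/2. If the SD is 1 at each ISI and the between-ISI correlation is ρ, the SD of the two-ISI mean is √((1 + ρ)/2). The standardised effect is therefore multiplied by 0.5/√((1 + ρ)/2).

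**3. Illustrative power.** Take α = 0.05 from section 4.3. Sidedness is not stated there; two-sided is assumed. A contrast with 80% power has z = 1.96 + 0.84 = 2.80. Power is approximately Φ(z − 1.96).

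| ρ (assumed) | z, effect at one ISI only: 2.80 × 0.5/√((1 + ρ)/2) | Power when averaged |
|---|---|---|
| 0 | 1.98 | 51% |
| 0.5 | 1.62 | 37% |
| 1 | 1.40 | 29% |

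The 80% reference assumes that the relevant ISI is known in advance and tested at unadjusted α. With Bonferroni over two ISIs the critical value is 2.24 and the reference becomes Φ(2.80 − 2.24) = Φ(0.56), about 71%.

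The opposite case uses the same formula with the effect equal at both ISIs, so z = 2.80/√((1 + ρ)/2):

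- ρ = 0: z = 3.96, power about 98%.
- ρ = 0.5: z = 3.23, power about 90%.

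Here averaging is unbiased and gains power.

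**4. Which term cures the dilution.** A simulation (40 runs, 30 against 30 subjects, all 32 cells) assumed a group effect of 0 at one ISI and 20 points at the other. The 30 controls come from section 5; the number of patients and all variances are assumptions.

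| Model | Group effect estimate | Residual variance |
|---|---|---|
| No ISI term | 10.4 | 331 |
| ISI main effect only | 10.4 | 305 |
| Subject type × ISI | 0.3 and 20.5 at the two ISIs | 278 |

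In balanced data a main effect of ISI takes variance out of the residual but leaves the averaged group estimate unchanged. Only the interaction recovers the two separate effects.

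**The case against.** The strongest reply is that the plan never says the ISIs are pooled. Amplitudes are computed by ISI, so an analysis at each ISI, or at one chosen ISI, is compatible with the text. The plan also does not always model every level it acquires. Section 4.1.4 varies the conditioning intensity for short-interval inhibition from 30 to 80% of motor threshold, while the corresponding model in section 4.3 uses 60% and 80% only. And the values 2 ms and 10 ms appear only in the resting model sentence. This stands as a limit: averaging is what the written model does if both ISIs are entered, not a declared intention. It does not remove the problem, since no sentence restricts aIHI to one ISI or plans to analyse it by ISI.

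It is also fair that the harm is conditional, that the case of no effect at one ISI is the extreme one, and that an 80% reference without multiplicity correction flatters the alternative. All of this is accepted and reflected in the figures above.

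A reader might infer two further consequences that the documents do not support:

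- **That the within-subject covariance is misspecified.** Section 4.3 says that within-subject correlation will be modelled and fixes no structure for aIHI, so no stated structure can be called wrong.
- **That resting and active IHI cannot be compared at a matched ISI.** Both are computed by ISI, and no such comparison is planned.

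Nor can the resting model be held up as a complete template. It lists ISI but states no interaction between ISI and subject type.

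**Conclusion.** The omission is clear on the text: aIHI is acquired at more than one ISI, and its model has no ISI term. Fitted as written to both ISIs, the model leaves ISI variation in the residual and reports effects averaged over ISIs. In balanced data, an effect confined to one ISI is estimated at half its size; an effect equal at both is not biased.

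A reader might take the fall from 80% to between 51% and 29% as the expected loss in this study. The documents do not support that. They give no aIHI effect size, SD or stroke sample size, and nothing in them shows that the group effect differs by ISI. Those figures are a worst case, and the fairer reference for a two-ISI analysis is about 71%.

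The importance is moderate. aIHI is one of several physiological measures under Specific Aim 1, it is not designated primary, and the list of TMS outcomes in the Study #2 analysis paragraph does not name it. The change is still worth making, because a better model is available from data that will be collected anyway.

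**What to change.** In section 4.3, add ISI (2 ms, 10 ms) to the aIHI model as a repeated-measures factor, together with ISI × subject type and ISI × time after the go signal. Report ISI-specific contrasts under the multiplicity correction already planned for post-hoc analyses. Adding ISI as a main effect alone is not enough: it would reduce residual variance but leave the dilution in place.

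If only one ISI is meant to be analysed, name it in section 4.3, give the reason, and reconcile this with the acquisition text in section 4.1.4.

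The cost is a few extra model terms and the correction for the added contrasts. No new data, visits or stimuli are needed.

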#### **4.4. Studies pertaining to Specific Aim #2: *Determine the role of contralesional M1 in motor performance during the post stroke recovery process***

In two studies (Study 1 and 2) we will test the effect of contralesional M1 transcranial magnetic stimulation on the subject's performance in a manual pointing task (4 different level of complexity, Presentation®) using either the paretic or the non-paretic hand in a counterbalanced randomized order and measures of motor excitability (IHI, SICI, MT, SRC, see above for details). To accomplish the goal of each study, a total of 6 experiments will be conducted in a randomized counterbalanced order. In Study 3 we will implement prediction and classification models to determine the predictive roles of variables measured in specific aim 1 on the supportive/detrimental role of cl\_M1 derived

from the effect of M1 downregulation by rTMS (Specific aim 2, study#1).

Study #1: Role of cl\_M1 on motor performance. In all subjects, we will test the effect of 1 Hz rTMS and sham cl\_M1 stimulation on the subject's performance in a pointing task of increasing difficulty using either the paretic or the non-paretic hand in a counterbalanced randomized order. Specifically, as previously described by our group in detail (Butefisch et al. 2003; Butefisch et al. 2008) rTMS at 90% MT will be used to decrease cl\_M1 function using a rapid Magstim (Magstim Company, UK). Briefly, coil position will be monitored online using Brainsight. EMG activity will be recorded from the ECU and other control muscles with the settings already detailed in Specific Aim 1. After determining the MT in the ECU hot spot (Rossini et al. 1994b), rTMS will be applied through the air-cooled figure-of-eight coil at 90% MT and 1 Hz frequency for 15 min (Butefisch et al. 2009). The effects will be compared to Sham stimulation applied at similar intensity and frequency (Butefisch et al. 2009). An additional two visits will be conducted for healthy subjects that include a repeat of the study measures described in specific aim 1 but we will stimulate at 80% rTMS to explore the effects compared to 90% rTMS and these visits will take the standard amount of time of 2-3 hours per visit. Preliminary data demonstrated different effects of different intensities and this needs to be confirmed in this population.

Study #2: Effect of transient disruption of cl\_M1 on M1 excitability and IHI. In all subjects, we will test the effect of cl\_M1 stimulation on the outcomes of MT, SRC, SICE and IHI in both motor cortices one month post stroke. All measurement will be repeated 6

months after infarction. The data will be compared to the results of healthy age matched controls to establish abnormality.

*Statistical analysis:* The statistical tests performed in this section will mirror those in the specific aim 1 with the addition of repeated measures factors specifying acquisition time (pre- or post-rTMS stimulation) and time post-stroke (1 and 6 months). The mixed-models will investigate the effect of cl\_M1 stimulation on TMS outcomes MT, SRC, SICE, rHI over time post-stroke. Additionally, we will use the mixed model to assess the effects of cl\_M1 excitability (SICE from SA #1) and cl\_M1 activation (number of activated voxels and % signal change within ROI) on rTMS-related changes in TMS measures.

Study #3: Identify biomarkers in the subacute and chronic phase of stroke that predict either the supportive or detrimental role of contralesional M1 as determined by responses to specific intervention protocols. In this study, we will implement prediction and classification models to determine the predictive roles of variables in SA #1 on the supportive/detrimental role of cl\_M1 derived from the effect of M1 downregulation by rTMS (SA#2, study#1). Specifically, we will train (and test) a binary classifier to predict subjects' responses (positive or negative) to rTMS (down regulation and sham) at 1 and 6 months post-stroke based on sets of predictors defined by SAs # 1 & 2. The association between the set of predictors and the binary response will be established during an iterative cross-validation process involving training and testing, in which different data are used to establish a predictive model and to evaluate its performance. We will assess performance using standard measures of prediction accuracy such as sensitivity,

specificity, positive predictive value, and negative predictive value. We will employ and compare multiple modeling techniques such as the Elastic Net, logistic classifier, and Bayes classifiers. Developing and optimizing the classifiers will identify subsets of measures that have the greatest predictive power for forecasting the role of cl\_M1.

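### Aim 2 randomises and counterbalances the order of six experiments, but no listed model has a session-position term, and the 80% visits are not stated to be part of that order

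*Combined protocol and SAP*

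**What the plan says.** Section 4.4 sets up Aim 2 as a within-subject comparison. For each study "a total of 6 experiments will be conducted in a randomized counterbalanced order", and the pointing task is done "using either the paretic or the non-paretic hand in a counterbalanced randomized order". The comparator for 1 Hz stimulation is sham.

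The Aim 2 analysis, given under Study #2, mirrors the Aim 1 models and adds "repeated measures factors specifying acquisition time (pre- or post-rTMS stimulation) and time post-stroke (1 and 6 months"). The Aim 1 factors in section 4.3 are subject type, stimulated hemisphere or direction of inhibition, conditioning intensity, interstimulus interval, time after the go signal, target size and stimulus intensity. On the dependence between repeated measures, section 4.3 says: "The analyses will incorporate models of within-subject correlations stemming from multiple measures on each subject". Section 6 only refers back to the individual sections, so no further term is defined elsewhere.

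The outcomes named for the Aim 2 models are excitability measures: "The mixed-models will investigate the effect of cl\_M1 stimulation on TMS outcomes MT, SRC, SICE, rHI over time post-stroke". No model is written out for pointing performance in Study #1. Study #3 takes a positive or negative response per subject from Study #1, without a rule for deriving it.

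For healthy subjects Study #1 adds: "An additional two visits will be conducted for healthy subjects that include a repeat of the study measures described in specific aim 1", where "we will stimulate at 80% rTMS to explore the effects compared to 90% rTMS". The text does not say when these visits fall or whether they are randomised with the others.

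**The concern.** In a multi-period crossover the order is balanced because performance or excitability may change with session number. The usual analysis then includes that factor. Here it is balanced in the design and absent from the listed models. Modelling within-subject correlation does not replace it: a correlation structure describes how a subject's residuals move together, whereas a session effect is a shift in the mean.

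Three things are at stake.

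- **Precision.** Session variation that could be removed stays in the residual of the active-minus-sham contrast.
- **Individual labels.** Balance is a property of the group. One patient has one order, and any session effect enters that patient's active-minus-sham difference in full.
- **80% versus 90%.** If the 80% visits follow the others, intensity and visit order cannot be separated. Because these visits repeat the Aim 1 measures, drift in excitability matters more there than practice on a task.

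**Working it through.** The documents give no effect size, SD, patient sample size or drift, so there is no figure of the plan's to reproduce. What follows is an illustration.

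**From the documents:** 6 experiments; significance level 0.05 (taken as two-sided); 30 healthy subjects, used as n because no patient number is given.

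**Assumed:** one active and one sham session among the six; a linear drift of g per session in the pre-to-post change, in SDs of the within-subject active-minus-sham contrast; no carry-over. A shift in session baseline that leaves the change untouched cancels and counts as g = 0.

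**Step 1, position difference.** Two given sessions can occupy 30 ordered pairs of positions. Differences of 1, 2, 3, 4 and 5 occur 10, 8, 6, 4 and 2 times. The mean difference is 0, so there is no average bias. The mean square is (10×1 + 8×4 + 6×9 + 4×16 + 2×25)/30 = 210/30 = 7.

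**Step 2, error variance without a session term.** The variance is multiplied by 1 + 7g². For g = 0.2 this is 1 + 7×0.04 = 1.28, so the SE is √1.28 = 1.13 times as large.

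**Step 3, power.** With n = 30, an effect of 0.53 SD gives 80% power when g = 0. Power was simulated with 20,000 cohorts per value of g and randomly drawn orders.

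**Step 4, label.** Suppose the label is the sign of active minus sham and the patient's true effect is 1 SD. The chance of the wrong sign is Φ(−(1 + g×d)), where d is the position difference. This is averaged over the 30 pairs, and also taken at the least favourable d = −5, which is 1 pair in 30.

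**Step 5, 80% versus 90%.** If the two extra visits are always seventh and eighth, their mean position is 7.5 against 3.5 for a session in the randomised six. The bias is (7.5 − 3.5)g = 4g. The false-positive rate comes from a noncentral t with 29 degrees of freedom and noncentrality 4g√30, holding the contrast SD at 1.

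| g (assumed) | Variance increase | Power, no term | Power, with position covariate | Wrong label, average | Wrong label, worst order | 80/90 bias | 80/90 false positive |
|---|---|---|---|---|---|---|---|
| 0 | 0% | 80.0% | 78.5% | 15.9% | 15.9% | 0 | 5% |
| 0.05 | 1.8% | 79.7% | 78.8% | 16.1% | 22.7% | 0.2 SD | 18% |
| 0.1 | 7% | 77.3% | 78.7% | 16.7% | 30.9% | 0.4 SD | 56% |
| 0.2 | 28% | 70.1% | 78.9% | 19.0% | 50.0% | 0.8 SD | 99% |
| 0.3 | 63% | 59.5% | 78.3% | 22.1% | 69.1% | 1.2 SD | about 100% |

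**Step 6, what the omission does to the SE.** Under exact counterbalancing the estimate's true spread does not depend on the session effect. Omitting the term only makes the reported SE too wide. Under randomly drawn orders, balanced only in expectation, the spread itself also grows.

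**Step 7, cost of the term.** Simulated with n = 30, randomly drawn orders and all six sessions fitted, five session terms raise the SE by about 1–2% when there is no drift.

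**Step 8, why visit number cannot rescue visits that are always last.** If 80% occurs only at positions 7 and 8, its indicator equals the sum of those two position indicators. A categorical visit term is then aliased with intensity. Separating them needs an assumed shape for the drift, such as linearity.

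**The case against.** The strongest case against has six parts.

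- **The pre/post factor removes baseline drift.** This stands. Only a session effect on the within-session change, or an analysis of post values alone, carries through.
- **Practice may be largely over.** Section 4.1.1 lets subjects practise the motor task at least a day before fMRI, and section 4.1.4 uses a pointing task in Aim 1. If these are the Aim 2 task and come first, a steep first-session gain is less likely. The documents do not settle this. A reader might assume a large early practice gain and infer a large loss of precision, but no figure in the plan supports that.
- **The listed factors are not a full specification.** The Study #2 list does not name active versus sham either, and pointing performance has no written model. The missing session term is therefore a gap to close and is not evidence of a deliberate choice.
- **The term could cost precision.** Fitting five session effects to only the active and sham sessions, under unbalanced orders, raises the SE by about 10% over exact removal. With all six sessions fitted the cost is the 1–2% above.
- **The label rule and session layout are not given.** This stands. The label figures hold only if the label uses the active and sham sessions. If conditions repeat across hands, averaging would reduce them.
- **The 80% comparison is exploratory and in healthy subjects only.** This also stands, although the same section says the intensity difference seen in preliminary data needs confirming. A reader might infer that the 80% visits lie outside the randomised order. The text calls them additional and is silent on their timing, so the supportable statement is that they are not stated to be in it.

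**Conclusion.** The omission is real and worth correcting. A reader might infer that the group active-versus-sham contrast is biased, but the randomised counterbalanced order prevents that, carry-over aside. What remains is a residual, and so an SE, larger than it need be, and no protection for individual labels that use the active and sham sessions.

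The size cannot be fixed from the documents. Under linear drift in the pre-to-post change it is negligible for the group contrast at 0.05 SD per session and material from roughly 0.2 SD, where power falls from 80% to about 70%. Averaged over orders, the added label error at 0.2 SD is modest (19.0% against 15.9%); the serious errors fall on patients with unfavourable orders. With no drift none of this arises.

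The 80% versus 90% comparison is the most sensitive part, but only if those visits come after the others.

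**What to change.** 1. Add session position, categorical and within each time point, as a fixed effect in every Aim 2 model, including a written-out pointing-performance analysis. Fit it on all sessions, not only the active and sham pair.
2. State the Study #3 rule and derive each patient's response from the session-adjusted change. This removes the average session effect; it cannot remove a patient's own departure from it.
3. State where the 80% visits fall. For healthy subjects not yet started, place them in the randomised order. Where they always came last, report 80% versus 90% as descriptive and order-confounded; a visit-number term cannot separate the two.

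The cost is about five degrees of freedom per time point (six positions less one), about 1–2% in SE if there is no drift, and a revised order list. No extra visits are needed. None of this takes a position on which intensity is right.
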